### 5.2 Screening Procedures

Informed consent will take place either at the Imperial Clinical Research Facility, or at the local addiction service within CNWL, or other HRA approved specified sites, as required. The local addiction service where participants are receiving treatment, and/or the participants' general practitioner will be notified of their patient's participation.

#### 5.2.1 Consent

The PIS and consent forms will be read through carefully with the participant. If they wish to participate, they will be informed that participation is entirely voluntary and that they can leave the study at any time without their decision affecting the treatment that they will be receiving. Written informed consent will be taken by a member of the research or clinical team under the supervision of the chief investigator.

Consenting participants will undergo enrolment and routine screening to ensure they are medically fit and eligible to take part. Members of the research team will discuss the study in detail, and the subject's eligibility to participate assessed against inclusion and exclusion criteria. A clinical member of the team will take a detailed clinical history of current and previous health and perform a physical examination to check for current health. In addition to eligibility assessment through history and examination, blood tests will be undertaken, where it is deemed clinically necessary e.g. if participant has a history of kidney/hepatic impairment that requires confirmation of current status.

Screening visits will last approximately 2-3 hours. For the majority of participants, the screening procedures will take place at the Imperial Clinical Research Facility (CRF) at Hammersmith hospital. However, to provide flexibility for our opiate dependent participants, the screening visit may be undertaken within our partner trust at Central and North West London NHS Foundation (CNWL) trust (CIPPres clinic), or certain aspects of screening (e.g. consent, questionnaires) may be completed at the local addiction service within CNWL, as applicable, to reduce the cognitive burden and increase study flexibility, acceptability and compliance.

Participants will undergo the following procedures at the screening visit:

#### 5.2.1 Pregnancy test

Female participants will undertake a urine pregnancy test.

### **5.2.2 Breath Alcohol Level**

Screening for alcohol content will be conducted with alcohol breath test. Additional random alcohol screens may be performed during the study at the Investigator's discretion.

### **5.2.3 Urine Drug Screen**

Urine will be screened for drugs of abuse including amphetamines, benzodiazepines, cannabinoids, cocaine, methadone, opiates. Participants will be assured that results of these tests (and all other information obtained in the study) are confidential and will not be reported to key workers, GP or participating addiction services.

### **5.2.4 Vital statistics and Vital signs**

Height, weight and body mass index will be measured. Vital signs will comprise systolic and diastolic blood pressure, pulse rate, body temperature and blood oxygenation.

### **5.2.5 Medical examination**

Medical examination will be assessed by structured interview as related to the eligibility criteria listed.

### **5.2.6 Physical Examination**

Physical examination will include assessments of the head, nose, throat, skin, thyroid, neurological, lungs, cardiovascular, abdomen, lymph nodes and extremities.

### **5.2.7 Respiratory Examination**

Participants will be asked about risk factors for respiratory disease e.g. history of persistent cough or breathlessness at rest, previous verified diagnosis of chronic obstructive pulmonary disease (COPD), hospital admission due to COPD, non-invasive ventilation for type 2 respiratory failure, use of inhalers for respiratory compromise, ventilation due to COVID-19, history of inhalation/smoking of substances e.g. heroin, tobacco, crack cocaine.

If further tests are clinically indicated to determine signs of current COPD or respiratory function, participants will undergo a 6 minute walk test with SpO2 monitoring, for signs of respiratory compromise.

If clinically indicated, participants will complete spirometry examination to measure forced expiratory volume/forced vital capacity (FEV1/FVC) ratio. Due to COVID-19 restrictions for aerosol generating procedures (AGPs), this may be undertaken outside or at home under guidance of the study team via video link.

### **5.2.8 Blood samples for clinical laboratory testing**

Given that blood sampling is required for the experimental visit, an assessment of venous access will be made. Blood samples will be collected via venepuncture if clinically indicated e.g. for full blood count, urea and electrolytes, and liver function tests. Venous access is a particular problem that is common in injecting heroin users, therefore failure to provide a blood sample will not exclude a participant as long as all other eligibility criteria are met and clinicians are satisfied that participation will be safe.

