## **2.6 Potential for CNS depressant effects- rationale for respiratory measures**

There are no formal RCT studies directly assessing the CNS depressant effects of baclofen in combination with opioids. A retrospective cohort study of opioid overdose found a small increased odds ratio for concomitant baclofen use compared with opioid use alone (Li et al., 2020), however those with substance use disorder were specifically excluded. There are also no specific reports of an interaction between baclofen and methadone specifically, although baclofen has been shown to potentiate opioid effects such as morphine-induced analgesia (Gordon et al., 1995) and fentanyl-induced anaesthesia ((Corli et al., 1984; Panerai et al., 1985) with iv or im dosing). The potential for a mechanistic interaction is plausible due to co-localisation of spinal GABA-B and opioid receptors in lamina II of the dorsal horn, an important site for nociceptive

processing in C fibre primary afferent neurones, although a supraspinal mechanism cannot be ruled out.

Baclofen alone can cause sedation and has been shown to cause respiratory depression at high doses. In alcohol dependence chronic baclofen was found to be associated with increased risk of all-cause hospitalization and mortality, particularly at high doses (>180mg/day, (Chaignot et al., 2018)). Again, those receiving OST were specifically excluded from the analysis.

In other studies of baclofen alone, a case series collected over 5 years identified signs of toxicity in 9 individuals suffering from severe renal impairment after taking a short course of baclofen (Chen et al., 1997). The authors noted that altered consciousness was the major presenting feature and that respiratory depression was relatively uncommon. A more recent observational study has suggested an association between respiratory depression and baclofen use in spasticity with chronic kidney disease, related to increased circulating baclofen levels (Mitsuboshi, 2021). Other studies mentioning incidence of respiratory depression have been in the context of overdose e.g. in adolescents consuming between 60 and >600mg baclofen in a non-lethal 'mass intoxication' (Perry et al., 1998).

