### **2.6.3 Cardiovascular effects**

Cardiovascular effects are not commonly reported in response to baclofen, except in studies of renal impairment or after very high doses e.g. in overdose (Nugent et al., 1986; Roberge et al., 1994). Evans et al reported a small effect of 80mg acute baclofen to increase heart rate (increase of 10 bpm) and blood pressure (121 to 125 mmHg) at 2 hours post dose, which returned to normal after 6 hours (Evans & Bisaga, 2009). In our acute study, we observed no overall significant effects on heart rate or blood pressure (Durant et al., 2018).

Methadone is reported to prolong QT interval, however there are no reports of QT prolongation following baclofen, therefore there is no indication that they are not safe to use together with respect to QT intervals.

We will monitor QT and cardiovascular parameters for signs of acute change after baclofen administration.

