#### **5.7.1 Baclofen in licensed indication**

For baclofen, BNF recommended maximum dose is 100mg/d for licensed indication of spasticity. Example SmPCs for generic baclofen can be found here:

Accord UK Ltd (10mg tablets)

<https://www.medicines.org.uk/emc/product/5728/smpc>

Advanz Pharma (10mg tablets)

<https://www.medicines.org.uk/emc/product/11781/smpc>

Mylan (10mg tablets)

<https://www.medicines.org.uk/emc/product/2594/smpc>

Baclofen is the only selective GABA-B agonist licensed for human use. Originally developed as a potential anti-epileptic in the 1920s, it was found to have anti-spastic effects and is currently used for the treatment of spastic movement, especially in instances of spinal cord injury, spastic diplegia, multiple sclerosis, and amyotrophic lateral sclerosis. It is an orally active *g*-aminobutyric acid (GABA) derivative, p-

chlorophenyl-gamma aminobutyric acid. Its primary action as an antispasticity agent is via simulation of GABAB-receptors resulting in depression of monosynaptic and polysynaptic reflex transmission. Baclofen increases K+ conductance resulting in postsynaptic inhibition and reduces Ca2+ influx and the release probability of excitatory transmitters (glutamate and aspartate) causing presynaptic inhibition in the brain and spinal cord (Katzung, 2009). Baclofen also exerts an antinociceptive effect and may act at supraspinal sites producing CNS depression. Baclofen may also modulate dopamine release in the mesocorticolimbic system by targeting neurons in the ventral tegmental area (Cruz et al., 2004).

Over its many years of use, baclofen has proven to be a very safe drug with few side effects. The main adverse effects are somnolence, dizziness, muscle weakness, and headache. Baclofen has good absorption after oral administration (75%), with peak serum concentrations achieved in 2–4 h. It is weakly bound (30%) to plasma proteins, and is eliminated primarily via the kidneys, 85% as the unchanged parent compound, with an estimated elimination half-life of 3-4 hours. The therapeutic serum concentration for spasticity is 0.08 to 0.4 microgram/ml.

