## **6.4 Eligibility Criteria**

### ***6.4.1 Inclusion Criteria***

1. Male or female
2. Aged over 21
3. Willing and able to comply with protocol

4. Able to read, comprehend and record information written in English
5. Capable of giving written informed consent, which includes compliance with the requirements and restrictions listed in the consent form.
6. Healthy as determined by a responsible physician, based on a medical evaluation which includes medical history, a physical examination, laboratory tests (if required), and a psychiatric evaluation. A volunteer with clinical parameters outside the reference range for the population being studied may be included, only if the investigators concur that the finding is unlikely to jeopardize either subject safety or study integrity.
7. DSM-5 diagnosis of current severe opioid use disorder
8. Treated with methadone substitution therapy and able to maintain the same stable dose for screening and experimental visit.
9. Ability to receive an acute dose of up to 90mg baclofen or up to 4800IU vitamin D (placebo).

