10. Participants are taking any medication that is contraindicated with baclofen or placebo (vitamin D3), or are hypersensitive to them or any of their excipients.
11. Participants that are taking any medication that in the opinion of the investigators may impact on the outcome measures during the experimental session.
12. Use of intermittent psychotropic medication which in the opinion of the investigators will interfere with subject safety or study integrity.
13. End stage or acute renal failure.
14. Severe chronic obstructive pulmonary disease (COPD) or Type 2 respiratory failure.
15. Pulse rate <40 or >100 BPM OR systolic blood pressure >160 and <100 and a diastolic blood pressure >95 and <60 in the semi-supine position.
16. Oxygen saturation <92% at rest
17. A screening ECG with a QTcB or QTcF > 500 msec or an ECG that is not suitable for QT measurements (e.g. poorly defined termination of the T-wave) and/or with another ECG abnormality which in the opinion of the study physician is clinically significant and represents a safety risk. Note that if the initial QTc value is prolonged, the ECG should be repeated two more times (with 5 minutes between ECG readings) and the average of the 3 QTc values used to determine eligibility.
18. Clinically significant head injury (e.g., requiring medical or surgical intervention) that in the opinion of the investigators, contraindicates their participation .
19. Active hepatitis or HIV.
20. Active peptic ulceration.
21. Significant current or past medical history that, in the opinion of the investigators, contraindicates their participation.
22. The subject has participated in a clinical trial and has received an investigational product within 30 days, 5 half-lives or twice the duration of the biological effect of the investigational product (whichever is longer) prior to the first experimental visit.

23. Pregnancy or breast-feeding
24. Unwillingness or inability to follow the procedures outlined in the protocol.

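### Kidney function is tested before dosing only when clinically indicated and severe non-end-stage impairment is not a named exclusion, so impaired baclofen clearance could go unrecognised; the likely harm is modest and a cheap check would close the gap

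*Combined protocol and SAP*

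**What the plan says.** **Testing.** Section 5.2.8: "Blood samples will be collected via venepuncture if clinically indicated e.g. for full blood count, urea and electrolytes, and liver function tests". Section 5.2.1 (Consent) gives as its example of clinical need "if participant has a history of kidney/hepatic impairment that requires confirmation of current status". Inclusion criterion 6 makes laboratory tests conditional, and the schedule in section 5.6 shows clinical blood sampling in brackets. Section 5.2.8 adds that a participant who cannot give a sample may still enter if the other criteria are met and clinicians are satisfied on safety. Blood on the experimental day is for baclofen, methadone and growth hormone (section 5.4.11).

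**Exclusion.** Criterion 13 reads "End stage or acute renal failure". No creatinine or eGFR limit appears. Criterion 21 lets investigators exclude on medical history at their discretion.

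**Why kidneys matter here.** According to section 5.7.1, baclofen "is eliminated primarily via the kidneys, 85% as the unchanged parent compound". Section 2.6 cites a case series that "identified signs of toxicity in 9 individuals suffering from severe renal impairment after taking a short course of baclofen", and an observational study linking respiratory depression with "baclofen use in spasticity with chronic kidney disease, related to increased circulating baclofen levels". Section 2.6.3: "Cardiovascular effects are not commonly reported in response to baclofen, except in studies of renal impairment or after very high doses". Section 7.1.1 states the aim that screening keeps out every person at risk of respiratory depression.

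**The concern.** The protocol treats reduced renal function as something that raises baclofen levels and is linked to toxicity, including the respiratory depression that section 2.10 calls the toxicity of primary concern. Yet no section requires a renal result before dosing. History, examination and physician judgement can pick up known or suspected disease, but not silent disease. Severe impairment short of end stage, even if found, is excluded only by judgement. The screening in section 5.2.7 is directed at the lungs, so the aim in section 7.1.1 is not fully met on the protocol's own evidence.

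What is at stake is the individual participant. With slower clearance, more drug remains when the 5 h supervision period ends, on top of methadone with a half-life of about 24 h (section 5.4.2).

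**Working it through.** The plan gives no figure to reproduce, so this is an illustration of size.

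**Inputs from the protocol**
- Renal share of elimination: 85% (5.7.1), read here as the share of clearance.
- Half-life: 2.7 to 3 h (5.4.3) and 3 to 4 h (5.7.1); values used are 2.7, 3 and 4 h.
- Time of peak: 88 to 102 min (5.4.3) and 2 to 4 h (5.7.1); values used are 88 min, 102 min, 2 h and 3 h.
- Supervision: 5 h (5.4.15). Maximum on baclofen: 48 (6.2).

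**Assumptions**
- Kidney function f is 0.5 or 0.25 of normal.
- One compartment, first-order absorption, linear kinetics; volume and absorption unchanged.

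**Formulas**
- Relative clearance = 0.15 + 0.85f. This gives 0.575 at f = 0.5 and 0.3625 at f = 0.25.
- A 3 h half-life becomes 3/0.575 = 5.2 h or 3/0.3625 = 8.3 h.
- C(t) is proportional to ka/(ka − k) × (exp(−kt) − exp(−ka·t)), with k = ln 2/half-life and ka solved from Tmax = ln(ka/k)/(ka − k). At the peak, C = exp(−k·Tmax) on the same scale.

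**One case in full (half-life 3 h, Tmax 88 min)**
- Normal: k = 0.231, ka = 1.512. C(5 h) = 1.180 × (0.3150 − 0.0005) = 0.371; peak = exp(−0.231 × 1.467) = 0.713; ratio 0.52.
- f = 0.5: k = 0.133. C(5 h) = 1.096 × (0.5146 − 0.0005) = 0.564, which is 1.52 times normal. Peak 0.791 at 1.8 h, which is 1.11 times normal.
- f = 0.25: k = 0.0838. C(5 h) = 1.059 × (0.6578 − 0.0005) = 0.696, which is 1.88 times normal. Peak 0.844 at 2.0 h, which is 1.18 times normal.

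**Half-life 3 h, Tmax 88 to 102 min**

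| | Normal | f = 0.5 | f = 0.25 |
|---|---|---|---|
| 5 h level as share of own peak | 52–57% | 71–76% | 82–86% |
| Share of total exposure after 5 h | 37–39% | 56–58% | 70–71% |

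**All 12 combinations of half-life and Tmax**

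| Impaired against normal | f = 0.5 | f = 0.25 |
|---|---|---|
| Peak ratio | 1.08–1.23 | 1.14–1.41 |
| 5 h level ratio | 1.28–1.58 | 1.45–1.99 |
| Own time of peak | 1.7–3.8 h | 2.0–4.6 h |
| Time at which the normal 5 h level is reached | 7.9–8.5 h | 11.8–12.7 h |

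The peak comes before 5 h in every combination. The grid stops at a normal Tmax of 3 h. At the 4 h upper end in section 5.7.1, the same formulas put the impaired peak at about 5.1 to 6.4 h, but the 5 h level is already 97% or more of that peak.

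**How many people.** The documents give no prevalence. Under assumed values of 1%, 2% and 5%, the chance of at least one case among 48 is 1 − (1 − p)^48 = 38%, 62% and 91%. With a prevalence near zero it is near zero.

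**The case against.** The strongest reply is that the protocol already handles prolonged effects. Section 5.4.15 has staff make sure that ill effects have worn off before the participant goes home, requires physician approval for discharge, and gives a 24-hour number for the study doctor. Section 3.4.6 extends the intervention-level window if symptoms persist, and section 5.5 adds a next-day call, with a second if sedation continues. These points stand and are the main reason the harm is modest. They respond to visible effects, however, and do not identify the participant beforehand.

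The cited evidence also differs from this setting. The 9 cases had severe impairment and took a short course, and section 2.6 notes that altered consciousness predominated while respiratory depression was relatively uncommon. The kidney-disease report concerns use in spasticity. Neither shows harm from one dose in silent moderate impairment.

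Conditional sampling is a reasoned choice, because section 5.2.8 expects poor venous access in this population. That supports accepting an existing record or a documented decision, but not leaving the question unasked.

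A reader might infer three stronger things:
- **That impairment would be missed.** The documents support only could. The kidney history in section 5.2.1 is an example, not the sole trigger; section 6.1 expects no substantial physical health needs; and section 7.1 lets the treating team raise concerns.
- **That 90 mg would act like a far larger dose.** Total exposure does rise 1/0.575 = 1.74 or 1/0.3625 = 2.76 times, but the modelled peak rises at most 1.41 times over the grid, and no document gives a concentration-effect threshold.
- **That the dose-toxicity analysis is invalid.** The model contains only the two doses, so a toxicity due to slow clearance would be read as a dose effect. But there may be no such participant, plasma baclofen is measured, and the Dose Setting Committee can overrule the model.

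**Conclusion.** The gap is real on the text: renal testing is conditional, and the named exclusion stops at end-stage or acute failure. Silent impairment, or severe impairment short of end stage, could therefore be missed, which falls short of the aim in section 7.1.1.

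Its size is modest. At the assumed 50% or 25% of normal function, the concern is a slower fall after a slightly higher peak, not a large overdose or effects that first appear after discharge. This rests on a simple model, on reading the 85% as a share of clearance, and on normal peak times up to 3 h. How a higher 5 h level translates into clinical effect is unknown, as is the number affected. It is a worthwhile low-cost precaution and does not reveal an error in any planned analysis.

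**What to change.** **Section 5.2.8.** Require a creatinine/eGFR result, from a recent clinical record or a screening sample, to be reviewed by the study physician before randomisation. If neither can be obtained, require a documented physician decision that states whether supervision is extended beyond 5 h. Align section 5.2.1 (Consent), inclusion criterion 6 and the bracketed schedule entry.

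**Exclusion criterion 13.** Change to: Severe renal impairment, end stage or acute renal failure.

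A record or screening sample is better than the experimental-day baseline draw, because that draw comes after randomisation and no section says that a rapid creatinine assay is available.

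**Cost.** At most one routine assay per participant, and none where a recent record exists. Venous access will sometimes fail, which the record and physician-decision routes cover. A few people may be excluded. No change to the dose-toxicity model is needed; plasma baclofen, already planned, can help interpret any dose-limiting toxicity.

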### **5.2.9 Psychiatric history, drug & alcohol history, demographics**

Psychiatric diagnoses according to DSM-5 criteria will be assessed by a psychiatrist, or by a study clinician and reviewed by a psychiatrist. Semi-structured interviews for assessment of sleep, alcohol, nicotine and drug use will be conducted, including a record of abstinence periods, recent on-top use. Demographic parameters will be captured in the case report form.

### **5.2.10 Questionnaire measures**

The following validated questionnaires will be administered to aid diagnoses and for characterising clinical status:

Mini International Neuropsychiatric interview (M.I.N.I.) (Sheehan DV et al., 1998)  
Beck Depression Inventory, BDI-II, (Beck et al., 1996)  
STAI; Spielberger State & Trait Anxiety Scale, (Spielberger et al., 1983)  
Visual Analogue Scales (VAS) of craving, anxiety  
Severity of Dependence Scale; SDS, (Gossop et al., 1995)  
Obsessive-Compulsive Drug Use Scale; OCDUS-H, (Franken et al., 2002).  
Fagerstrom test for nicotine dependence (Heatherton et al., 1991)  
Alcohol, Smoking, Substance Involvement & Screening Test (ASSIST)  
Alcohol current intake (AUDIT)  
Pittsburgh Sleep Quality Index (PSQI) (Buysse et al., 1989)  
Epworth Sleepiness Scale (ESS) (Johns, 1991)  
Restless legs severity scale (RLS scale), <https://www.rls-uk.org/diagnosis>

